10.5.4 Safety Analyses

Toxicity will be measured as a secondary outcome using CTCAE version 5.0. Adverse event monitoring will occur throughout the duration of the study and will be performed by research coordinators and investigators.

11.0 DATA SUBMISSION AND FORMS

REDCap (Research Electronic Data Capture) database system will be implemented to collect data for this study. The servers hosting REDCap are administered and supported by Indiana University's University Information Technology Services (UITS) and are physically located in IU's secured and environmentally structured data center on the IU Bloomington campus. To comply with HIPAA guidelines, physical, administrative, and technical safeguards and on ongoing risk management framework have been implemented and documented (NIST 800-53) to ensure the security and protection of the study data within the data center, the servers, and the database. REDCap is a software toolset developed by Vanderbilt University, with collaboration from a consortium of institutional partners, for electronic collection and management of research and clinical trial data. Indiana University has joined this consortium and has implemented REDCap within the Indiana University's central Information Technology Services (UITS) technical environment to enable rapid development and deployment of electronic data capture and reporting to support specific clinical and translational research projects. Access to the password-protected database will be limited to the investigators of this study, and any data that is distributed will be either de-identified or authorized by written permission from participants. All source documents are to remain in the patient's clinic file. All documents should be kept according to applicable federal guidelines. Clinical trial data in REDCap will be periodically monitored by the IU Simon Cancer Center Data Safety Monitoring Committee.

12.0 REGULATORY, ETHICAL, AND STUDY OVERSIGHT CONSIDERATIONS

12.1 Informed Consent Process

12.1.1 Consent Procedures and Documentation

Informed consent is a process that is initiated prior to the individual's agreeing to participate in the study and continues throughout the individual's study participation. Consent forms will be Institutional Review Board (IRB)-approved and the participant will be asked to read and review the document. The investigator or research personnel will explain the research study to the participant and answer any questions that may arise. A verbal explanation will be provided in terms suited to the participant's comprehension of the purposes, procedures, and potential risks of the study and of their rights as research participants. Participants will have the opportunity to carefully review the written consent form and ask questions prior to signing. The participants should have the opportunity to discuss the study with their family or surrogates or think about it prior to agreeing to participate. The participant will sign the informed consent document prior to any procedures being done specifically for the study. Participants must be informed that participation is voluntary and that they may withdraw from the study at any time, without prejudice. A copy of the informed consent document will be given to the participants for their records. The informed consent process will be conducted and documented in the source document (including the date), and the form signed, before the participant undergoes any study-specific procedures. The rights and welfare of the participants will be protected by emphasizing to them that the quality of their medical care will not be adversely affected if they decline to participate in this study.

12.2 Study Discontinuation and Closure

This study may be temporarily suspended or prematurely terminated if there is sufficient reasonable cause. If the study is prematurely terminated or suspended, the Principal Investigator (PI) will promptly inform study participants, the Institutional Review Board (IRB), and sponsor and will provide the reason(s) for the termination or suspension. Study participants will be contacted, as applicable, and be informed of changes to study visit schedule.

Circumstances that may warrant termination or suspension include, but are not limited to:

- Determination of unexpected, significant, or unacceptable risk to participants
- Demonstration of efficacy that would warrant stopping
- Insufficient compliance to protocol requirements
- Data that are not sufficiently complete and/or evaluable
- Determination that the primary endpoint has been met

Study may resume once concerns about safety, protocol compliance, and data quality are addressed, and satisfy the sponsor and/or IRB.

12.3 Confidentiality and Privacy

The study protocol, documentation, data, and all other information generated will be held in strict confidence. No information concerning the study or the data will be released to any unauthorized third party without prior written approval of the investigator.

Each subject in the database will be assigned a unique study identification (ID) number. Patient- derived material will be linked to patient clinical information through this study ID number. Data from the participant's medical record will be manually entered into the participant's de-identified study database and never stored in its original form, ensuring that the data cannot be traced back the actual participant in the event of a data breach. Data will be stored on the University's approved, encrypted back-up servers. The data will be maintained in the database for at least ten (10) years after collection. Records and/or data extracted from the database will be identified by the subject study ID number only and without any accompanying individually identifiable patient information. Thus, the code to the study identification numbers will be accessible only to the PI and authorized study personnel.

Study participant research data, which is for purposes of statistical analysis and scientific reporting, will be transmitted to and stored in a secure database. This will not include the participant's contact or identifying information. Rather, individual participants and their research data will be identified by the unique study identification number. The study data entry and study management systems will be secured and password protected. At the end of the study, all study databases will be de-identified and archived.

All paper study materials will be stored in a locked cabinet that will only be accessed by IRB approved staff. Only IRB approved staff will have access to data from the participant's medical records. All research activities will be conducted in as private a setting as possible.

The study monitor, principal investigator, study team, representatives of the Institutional Review Board (IRB), and regulatory agencies may inspect all documents and records required to be maintained by the investigator, including but not limited to, medical records (office, clinic, or hospital) and pharmacy records for the participants in this study.

13.0 ADVERSE EVENTS

13.1 **Definition of Adverse Events**

13.1.1 Adverse Event (AE)

An adverse event is defined as an untoward medical occurrence associated with the use of an intervention in humans, whether or not considered intervention related. An adverse event can be ANY unfavorable and unintended sign (e.g., an abnormal laboratory finding), symptom, or disease temporarily associated with the use of an intervention, whether or not considered related to the intervention (attribution of 'unrelated', 'unlikely', 'possible', 'probable', or 'definite'). Adverse events will be graded according to CTCAE version 5.0

13.1.2 Definition of Serious Adverse Events (SAE)

A serious adverse event is any untoward medical occurrence resulting in one or more of the following:

- 1. Results in death or ANY death occurring within 30 days of treatment
- 2. Is life-threatening (defined as an event in which the patient was at risk of death at the time of the event; it does not refer to an event which hypothetically might have caused death if it were more severe)
- 3. Requires inpatient hospitalization \geq 24 hours or prolongation of existing hospitalization

NOTE: Hospitalizations that are not considered SAEs are:

- Hospitalization planned prior to biopsy procedure
- Hospitalization < 24 hours in duration
- Hospitalization for elective treatment of a pre-existing condition unrelated to biopsy procedure.
- 4. Results in persistent or significant disability/incapacity
- 5. Is a congenital anomaly or birth defect
- 6. Is an important medical event (defined as a medical event(s) that may not be immediately life-threatening or result in death or hospitalization but, based upon appropriate medical and scientific judgment, may jeopardize the patient or may require intervention (e.g., medical, surgical) to prevent one of the other serious outcomes listed in the definition above). Examples of such events include, but are not limited to, intensive treatment in an emergency room or at home for allergic bronchospasm; blood dyscrasias or convulsions not resulting in hospitalization; or the development of drug dependency or drug abuse.

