2.3 Risk/Benefit Assessment

There is very minimal risk outside the standard of care as both treatment options are currently utilized and have category 2B recommendations from the NCCN. Expected toxicities of both treatment arms include fatigue and potential worsening of liver function.

The only added non-standard of care risk would be for RS patents surrounding their functional HIDA scan. The risks involved in a HIDA scan are minimal. They include the following:

- 1. Radiation exposure; a very small amount of radioactive material is used and the radiation exposure is well below the level that causes adverse effects.
- 2. Allergic reactions to the radioactive material; however, this is extremely rare, without documented cases.
- 3. Discomfort, bruising or rash at the injection site or discomfort while lying on the table for the required amount of time for the scan.

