5.0 STUDY POPULATION

5.1 Inclusion Criteria

In order to be eligible to participate in this study, an individual must meet all of the following criteria:

- 1. Ability to provide written informed consent and HIPAA authorization
- 2. Stated willingness to comply with all study procedures and availability for the duration of the study
- 3. Male or female, aged ≥ 18 years at time of informed consent
- 4. Solitary HCC (≤3 cm) diagnosed by imaging (LI-RADS 4-5) or histology
- 5. Childs-Pugh score ≤ 7
- 6. ECOG performance status 0-1
- 7. Tumor location/characteristics eligible for either SBRT or Y90 therapy as deemed by local tumor board
- 8. Adequate organ function defined as:
 - a. serum bilirubin < 4.0 mg/dL
 - b. albumin > 2 g/dL

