7.0 STUDY INTERVENTION

7.1 Study Interventions

There are two comparative intervention arms, both of which are currently standard-of-care.

7.1.1 Selective transarterial radioembolization (Radiation Segmentectomy (RS)):

This therapy arm involves two separate steps, a planning/mapping arteriogram and a therapy delivery. The planning arteriogram will be performed to confirm arterial anatomy is acceptable for RS (\leq 2 segment delivery) and that lung shunting is not too high to preclude treatment with RS. Once confirmed, patients will return for RS (within 45 days of mapping). Dose will be calculated based off the desired treatment volume using pre-treatment cross-sectional imaging. The desired segmental dose will be calculated to be \geq 200Gy. RS will be performed by one of three separate interventional radiologists with experience in radioembolization. Actual administered activity and location of dose administration will be recorded.

7.1.2 Stereotactic Body Radiation Therapy (SBRT):

SBRT will be delivered with linear accelerator-based photon beams with either fixed angle non-coplanar fields or dynamic arcs. For treatment planning, CT simulation with triple phase IV contrast would be performed in the treatment position (supine, arms up). Tumor motion management would be assessed with 4D CT through the breathing cycle. Abdominal compression or breath-hold may be used at physician discretion for diaphragmatic excursion of 1cm or more. Available pre-treatment diagnostic imaging will be fused with the planning CT by deformable registration to assist in target and normal tissue delineation. An internal target volume (ITV) will be generated to account for tumor movement during breathing cycle. Finally, a planning target volume (PTV) will be an expansion of 3-5mm from the ITV. For Child Pugh A patients, prescription dose will either be 5000cGy in 5 fractions delivered every other day or 4800cGy in 3 fractions delivered twice weekly. For Child Pugh B patients, prescription dose of 4000cGy in 5 fractions delivered every other day. Inverse planning will be used. 95% of the PTV or more will receive at least 100% of the prescription dose. Normal tissue dose constraints for each dose level will be respected with acceptable deviations permitted as outlined in appendix VII. Patients will be seen at least once per week by a clinician to grade toxicities, with on- treatment labs (CBC, CMP, INR) each week.

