13.4.2 Reporting the IUSCC Data Safety Monitoring Committee

Regardless of study sponsorship, the study team must enter all initial and follow-up SAE, expedited, and noncompliance reports into OnCore® for review by the DSMC chair and/or coordinator. Expedited reports may include IRB Prompt Report Forms and additional SAE forms as required by the sponsor. When follow-up information is received, a follow-up report should also be created in OnCore®. This DSMC reporting requirement is in addition to any other regulatory bodies to be notified (i.e. IRB, FDA, pharmaceutical company, etc.). The DSMC chair and/or coordinator will review all SAE, expedited, and noncompliance reports monthly and findings will be reported to the full DSMC quarterly. See section 14.5 for additional details

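### Two of the three hospitalisation exemptions in the SAE definition (13.1.2) refer to a biopsy the trial does not perform: one has no reference point, and the other does not exclude elective admissions related to the arteriogram, Y-90 or SBRT.

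*Combined protocol and SAP*

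**What the plan says.** Section 13.1.2 of the combined protocol and SAP lists six criteria, any one of which makes an event serious. The third is inpatient hospitalisation of at least 24 hours, or prolongation of an existing stay. A note under it lists three kinds of admission that do not count:

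- "Hospitalization planned prior to biopsy procedure"
- "Hospitalization < 24 hours in duration"
- "Hospitalization for elective treatment of a pre-existing condition unrelated to biopsy procedure"

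The interventions are set out in 7.1: "There are two comparative intervention arms, both of which are currently standard-of-care". For radiation segmentectomy (RS), 7.1.1 adds: "This therapy arm involves two separate steps, a planning/mapping arteriogram and a therapy delivery". The other arm, SBRT, is described in 7.1.2. Tissue sampling is implied in one place only, inclusion criterion 4 in 5.1, where the tumour may be "diagnosed by imaging (LI-RADS 4-5) or histology".

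**The concern.** An exemption from SAE status should rest on events that occur in the trial. Here two of the three rest on a procedure that is not part of it. An investigator who applies the text literally has no date from which to judge whether an admission was pre-planned, and has a relatedness test that excludes nothing.

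The elective bullet matters more, because of who is enrolled and what is expected to go wrong. Section 2.2 says most patients with HCC have chronic liver disease. Section 2.3 says: "Expected toxicities of both treatment arms include fatigue and potential worsening of liver function". A scheduled admission for underlying liver disease that treatment has made worse is thus a foreseeable event, and it fits the wording of the exemption. At stake is whether that event is reported through the SAE route or only as an ordinary adverse event.

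**Working it through.** No arithmetic bears on the finding itself. The check sets the exemptions beside the trial's procedures and safety rules.

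**1. Is there a biopsy?** The Schedule of Events, 7.1.1, 7.1.2 and 8.1 list the mapping arteriogram, Y-90 delivery, CT simulation, SBRT, functional hepatobiliary scan, CT or MR, laboratory tests, examinations and questionnaires. None is a biopsy, and the word occurs only in the two bullets of 13.1.2. Histology in 5.1 is one optional route to a diagnosis made before enrolment. Elsewhere section 13 speaks of treatment, intervention or study procedures, so the biopsy wording does not match its own section.

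**2. What does the elective bullet exempt?** It has three conditions: the admission is elective, it treats a pre-existing condition, and it is unrelated to a biopsy. With no study biopsy, the third is met by essentially every on-study admission, so only the first two do any work.

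**3. How does each kind of admission fall out under the hospitalisation criterion?**

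| Admission | Exempt as written? |
|---|---|
| Unplanned, 24 hours or more, complication of Y-90 or SBRT | No; remains an SAE |
| Elective, 24 hours or more, new condition | No, unless pre-planned, which cannot be judged |
| Elective, 24 hours or more, pre-existing condition, made necessary by Y-90 or SBRT | **Yes, by the elective bullet** |
| Arranged before consent, 24 hours or more, elective treatment of a pre-existing condition | Yes, by the elective bullet |
| Arranged before consent, 24 hours or more, any other reason | Undetermined: the pre-planned bullet has no anchor |
| Any stay under 24 hours | Yes, by the duration bullet |

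The third row is the gap. The fifth is the residue left by the missing anchor.

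**4. What is lost with the SAE label?** Section 14.5 requires OnCore entry within 1 business day. Section 13.4.2 says: "The DSMC chair and/or coordinator will review all SAE, expedited, and noncompliance reports monthly", with findings going to the full committee quarterly. Section 13.4.1 has SAEs that do not need prompt reporting go to the IRB at continuing review.

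**5. What remains without it?** Section 13.3 requires all adverse events to be documented whatever their relationship, and treats deterioration of a baseline condition as an adverse event. The other five criteria in 13.1.2 still apply, including the one for important medical events. Section 14.0 has monthly study-team review. Section 14.1 has annual DSMC review of toxicity, and immediate notice to the DSMC chair if grade 3 or higher events exceed the reference rate.

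**6. Is any endpoint touched?** The primary endpoint is recruitment and screen failure. The toxicity endpoint in 4.2 counts CTCAE grade 4 or higher events at least possibly related to treatment, so it depends on grade and attribution, not on seriousness. Neither changes.

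**7. One caveat on step 5.** Section 13.3 stops recording non-serious events 7 days after the 6-month visit and SAEs at 30 days. Section 13.4 and footnote H of the Schedule of Events give 30 days for all. If 13.3 governs, an admission that loses SAE status and begins on days 8 to 30 after that visit might not be recorded. That conflict needs reconciling in its own right.

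**The case against.** The best defence is that this is leftover wording which staff will read as the study procedure, and that other text closes most of the gap. Liver disease that worsens on study is an adverse event under 13.3, so it is arguably no longer merely a pre-existing condition. A serious deterioration can still qualify under the important-medical-event criterion. The DSMC reads data directly from OnCore and REDCap (14.3), so an event labelled non-serious is not hidden from it.

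Much of this stands, and it limits the consequence largely to the speed and route of review. It does not settle the wording. Section 13.3 governs recording as an adverse event; 13.1.2 does not say that the elective exemption lapses when the condition worsens. Reading the biopsy as the study procedure also leaves the reference date open: consent, mapping, Y-90 delivery or first SBRT fraction. On the column limits in the Schedule of Events, enrolment and treatment can be 30 + 45 = 75 days apart (30 + 30 = 60 days for RS under footnote C), while events are recorded from consent. Two readers could classify the same admission differently.

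A reader might also infer three stronger things that the documents do not support:

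- **That treatment-related admissions in general escape SAE status.** Only elective ones for a pre-existing condition do.
- **That pre-planned admissions must now all be reported.** Those that are elective treatment of a pre-existing condition, or last under 24 hours, stay exempt through the other bullets. A diagnostic biopsy may also supply a date in patients diagnosed by histology.
- **That the comparison of the arms is distorted by some number of percentage points.** The plan analyses no proportion of patients with an SAE, so there is no such statistic to shift.

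**Conclusion.** The point holds as a wording error in an operative safety rule. The pre-planned exemption has no usable anchor. The elective exemption is usable but too broad, because it does not exclude admissions related to the planning arteriogram, Y-90 or SBRT.

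The practical effect is confined to elective stays of 24 hours or more for a pre-existing condition that meet no other SAE criterion. These can lose the expedited entry and monthly SAE review, but not all oversight. The documents give no expected number of such admissions, so the size cannot be stated as a rate.

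The conclusion assumes that 13.1.2 is applied as written and that no separate manual redefines the biopsy wording; the documents mention none. It is worth correcting at the next amendment and gives no reason to doubt the planned analyses.

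**What to change.** Replace the two bullets in 13.1.2 with text to this effect:

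- *Admission already planned before informed consent was given.*
- *Elective admission to treat a condition present at consent, provided that the condition has not worsened since consent and the admission is unrelated to the planning arteriogram, Y-90 administration or SBRT.*

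The first gives every participant the same reference date, and it matches the start of event recording in 13.3. The second restores a relatedness test against the procedures actually performed and carries the deterioration rule of 13.3 into the SAE definition. The bullet on stays under 24 hours needs no change for this purpose.

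The cost is two lines in an amendment and some added reporting, since a few more elective admissions may be entered as SAEs. No endpoint, sample size or analysis changes.

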13.1.3 Determining Attribution to the Intervention(s)

Attribution is an assessment of the relationship between the AE and the medical intervention. CTCAE does not define an AE as necessarily "caused by a therapeutic intervention". After naming and grading the event, the clinical investigator must assign an attribution to the AE using the attribution categories in Table 2 below.

Table 2: Determining Attribution

Relationship	Attribution	Description
Unrelated to investigational	Unrelated	The AE is clearly NO T related
intervention	Unlikely	The AE is doubtfully related
	Possible	The AE may be related
Related to investigational intervention	Probable	The AE is likely related
micer vention	Definite	The AE is clearly related

13.2 Expectedness

The principal investigator will be responsible for determining whether an adverse event (AE) is expected or unexpected. An AE will be considered unexpected if the nature, severity, or frequency of the event is not consistent with the risk information previously described for the study intervention.

